Multiplicity will be adjusted for the primary endpoint and the two key secondary endpoints on the analysis of subjects with baseline blood eosinophils \geq 220/ μ L for the comparisons of 30mg vs. placebo and 100mg vs. placebo according to a gatekeeping procedure (see section 8.5). Multiplicity will also be adjusted for the primary endpoint and the two key secondary endpoints on the analysis of subjects with baseline blood eosinophils \geq 220/ μ L for the comparisons of 10mg vs. placebo according to a serial gatekeeping procedure (see section 8.5).

The study will recruit subjects with blood eosinophil counts \geq 220/ μ L and <220/ μ L at a ratio of approximately 2:1 and the study is powered for the primary efficacy analysis of the subjects with blood eosinophils \geq 220/ μ L. For the primary endpoint annual COPD exacerbation rate, 348 subjects with baseline blood eosinophil counts \geq 220/ μ L per treatment arm (1392 total) will need to be randomised to achieve 90% power of detecting a 30% reduction in both the

30mg and 100mg benralizumab dose groups versus placebo after multiplicity adjustment. This calculation has assumed two-sided 4% alpha level test, an annual placebo rate of 0.93 events/subject (1.0 events/subject/56 weeks), a negative binomial shape parameter of 0.4, and a dropout rate of 10%. The sample size calculation is based on simulations and has accounted for the power loss from a proposed futility analysis. According to the approximately 2:1 ratio, the study will also enrol 174 subjects/arm (696 total) with baseline blood eosinophil counts $<220/\mu\text{L}$. An additional 20 subjects/arm will also be recruited to the 220-299/ μL cohort to better characterize patients within this cohort. This addition results in 368 subjects/arm in the $\geq 220/\mu\text{L}$ cohort (1472 total). A total of 2168 subjects are expected to be randomised in the study. Details of the estimated numbers of recruited subjects/arm in each cohort ($<220/\mu\text{L}$, 220-299/ μL , $\geq 300/\mu\text{L}$) are described in the SAP.

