1.2 Rationale for study design, doses and control groups

The final results of study MI-CP196 support conducting this Phase 3 study in patients with COPD with severe and very severe disease, treated with double (ICS/LABA, LABA/LAMA) and triple therapy (ICS/LABA/LAMA), who have elevated peripheral eosinophils. The greatest improvements in the annual exacerbation rate were observed in patients with increasing blood eosinophils (specifically ≥ 200 and $\geq 300/\mu\text{L}$) based on a pre-specified subgroup analysis (predose FEV₁ and health-related quality of life as measured by SGRQ-C). In patients with low eosinophil counts ($< 300/\mu\text{L}$), the exacerbation signal was not commensurate with what was observed in the high eosinophil group, and the exacerbation rate was not favourable for benralizumab, although the changes in FEV₁ and SGRQ-C were directionally similar to the high eosinophil group.

The clinical development program for benralizumab is designed to evaluate benralizumab's ability to reduce the COPD exacerbation rate in patients with moderate to very severe COPD.

The proposed Phase 3 subject populations are patients with moderate to very severe COPD, as evidenced by a post-bronchodilator FEV₁ >20% and ≤65% of predicted normal (GOLD 2013).

It was not considered appropriate to include patients with mild to moderate disease without exacerbations, or those being treated with single therapy. This is similar to the population explored in recent trials such as SPARK (Wedzicha et al 2013), which essentially evaluated the effect of triple versus double therapy in a severe to very severe patient population. Patients on monotherapy have several therapeutic options available before a biologic becomes part of their therapeutic options.

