The proposed benralizumab Phase 3 study will evaluate the efficacy and safety of benralizumab in patients who are uncontrolled despite standard of care therapies (double such as ICS/LABA, LABA/LAMA or triple such as ICS/LABA/LAMA) as evidenced by 2 or more moderate exacerbations or 1 or more severe exacerbation(s) in the previous year. Moderate exacerbations are defined as those requiring treatment with systemic steroids and/or antibiotics. Severe exacerbations are defined as those requiring a COPD related hospitalization or result in death. Hospitalization will be further defined as an inpatient admission ≥24 hours in the hospital, in an observation area, the emergency department or other equivalent healthcare facility depending on the country and healthcare system.

Subjects in this Phase 3 study will be stratified by country and blood eosinophil levels (≥300/μL or <300/μL) with a blood eosinophils boundary of ≥220/μL used for the primary and secondary efficacy analyses. Randomization will be capped at the study level for the baseline eosinophil cohorts (<220/μL, 220-299/μL, ≥300/μL) in order to keep predefined cohort sample size and approximately 2:1 ratio of subjects above and below the boundary of 220/μL.

Based on the efficacy observed in CP196 and recent data in the literature (Pascoe S et al 2015), the primary endpoint will be powered and conducted in subjects with blood eosinophil count ≥220/μL. Subjects with lower blood eosinophils levels (<220/μL) will be included to assess the benefit:risk relationship of benralizumab in COPD patients with a broad range of blood eosinophil levels. Descriptive statistics will be used to assess efficacy in COPD subjects across a broad spectrum of eosinophil levels as detailed in the SAP in order to better identify patients who are likely to benefit from benralizumab and also to evaluate inflection points for efficacy and safety to better define which patients need to be treated with this compound.

Three dose levels 10, 30 and 100 mg Q8W benralizumab will be evaluated in this Phase 3 study in COPD subjects, based on PK and eosinophil modelling, observed incidence of ADA, clinical efficacy, and safety.

Since only one dose level was investigated in Study MI-CP196, the dose-efficacy relationship of benralizumab in COPD has not been fully evaluated. Simulations indicate that the Q12W regimen is associated with a broader distribution of peripheral blood eosinophil counts. This

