For the comparison of the 10mg dose group and placebo in subjects with baseline blood eosinophils $\geq 300/\mu\text{L}$, multiplicity will be adjusted for the testing of the primary and two key secondary endpoints using a serial gatekeeping procedure (Dmitrienko and Tamhane 2007). In the procedure the primary endpoint will be tested at 0.05 level for the comparison of the 10mg dose group and placebo. The two secondary endpoints will be tested using a Holm procedure at the 0.05 level for the comparison of the 10mg dose group and placebo only if the test for the primary endpoint is significant at 0.05 level.

In summary the FWER will be strongly controlled for the comparison of 30mg and 100mg vs. placebo at 0.05 on testing of the primary endpoint and two key secondary endpoints. The FWER will also be strongly controlled for the comparison of 10mg vs. placebo at 0.05 on

testing of the primary endpoint and two key secondary endpoints. The FWER will not be strongly controlled at 0.05 for the testing of the primary endpoint and two key secondary endpoints across all three doses.

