8.5.1 Primary analysis method(s)

The primary efficacy variable is the annual COPD exacerbation rate and the primary analysis is to compare the annual COPD exacerbation rate of each benralizumab dose group with placebo in subjects with baseline blood eosinophil counts $\geq 220/\mu\text{L}$.

For each of the three benralizumab dose groups, the null hypothesis is that the exacerbation rate on benralizumab is equal to the exacerbation rate on placebo. The alternative hypothesis is that the exacerbation rate on benralizumab is not equal to the exacerbation rate on placebo, i.e.:

H₀: Rate ratio (benralizumab vs. Placebo) = 1

H_a: Rate ratio (benralizumab vs. Placebo) \neq 1

Exacerbation rate in each of the three benralizumab dose groups will be compared to exacerbation rate in the placebo group using a negative binomial model. The response variable in the model will be the number of COPD exacerbations over the 56-week treatment period. The model will include covariates of treatment group, eosinophil cohort (220-299/ μL or $\geq 300/\mu\text{L}$), country, background therapy (ICS/LABA, LABA/LAMA, or ICS/LABA/LAMA), and the number of exacerbations in the year before the study. The logarithm of the follow-up time will be used as an offset variable in the model.

The estimated treatment effect (i.e., the rate ratio of benralizumab versus placebo), corresponding 95% confidence interval (CI), and two-sided p-value for the rate ratio will be presented. In addition, the exacerbation rate and the corresponding 95% CI within each treatment group will be presented.

In addition, the exacerbation rate will also be summarized in subjects with baseline blood eosinophil counts $< 220/\mu\text{L}$, $< 150/\mu\text{L}$, 150-219/ μL , 220-299/ μL , 300-449/ μL , and $\geq 450/\mu\text{L}$ separately for descriptive purpose only.

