8.5.2 Secondary analysis methods

8.5.2.1 Analysis methods for secondary efficacy variables

Key secondary efficacy endpoints in this study are:

- Change from baseline in pre-dose/pre-bronchodilator FEV₁ at Week 56
- Change from baseline in SGRQ total score at Week 56

Other secondary efficacy endpoints include

- Proportion of subjects with ≥ 1 COPD exacerbation

- Time to the first COPD exacerbation
- Proportion of subjects with ≥ 4 -point decrease (improvement) in SGRQ total score at Week 56
- Annual rate of COPD exacerbations that are associated with an emergency room visit or a hospitalization
- Annual rate of hospitalizations, annual rate of hospitalizations and emergency room visits combined, annual rate of unscheduled outpatient visits including unscheduled visits to study centres and all unscheduled healthcare encounters due to COPD
- Rescue medication use (average puffs/day)
- Number of nights with awakening due to COPD and requiring rescue medication
- Change from baseline in E-RS total score and domain scores at Week 56
- Area under the curve (AUC) of E-RS total score
- BDI/TDI
- CAT
- EXACT-PRO

All the secondary efficacy endpoints will be analyzed in subjects with baseline blood eosinophil counts $\geq 220/\mu\text{L}$. In addition, the two key secondary endpoints will also be summarized in subjects with baseline blood eosinophil counts $< 220/\mu\text{L}$, $< 150/\mu\text{L}$, $150-219/\mu\text{L}$, $220-299/\mu\text{L}$, $300-449/\mu\text{L}$, and $\geq 450/\mu\text{L}$ separately for descriptive purpose only.

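### Section 8.5 runs the error-controlled 10 mg versus placebo procedure in subjects with at least 300/µL, while the synopsis (citing 8.5), 8.5.1 and 8.5.2.1 place the same endpoints in at least 220/µL

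*Protocol*

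**What the plan says.** Section 8.5 sets out two families of tests. The 30 mg and 100 mg family is defined in subjects with at least 220/µL. The paragraph on 10 mg begins "For the comparison of the 10mg dose group and placebo in subjects with baseline blood eosinophils $\geq 300/\mu\text{L}$, multiplicity will be adjusted". It tests the exacerbation rate at 0.05 and then, if that is significant, FEV1 and SGRQ by Holm at 0.05. The section concludes: "The FWER will also be strongly controlled for the comparison of 10mg vs. placebo at 0.05".

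The other current passages on these endpoints say something different:

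- The synopsis (Statistical methods) describes the same serial gatekeeping procedure in subjects with "baseline blood eosinophils \geq 220/ μ L for the comparisons of 10mg vs. placebo" and sends the reader to section 8.5.
- Section 8.5.1 gives the primary analysis as being to "compare the annual COPD exacerbation rate of each benralizumab dose group with placebo in subjects with baseline blood eosinophil counts $\geq 220/\mu\text{L" or more, with hypotheses for all three doses.
- Section 8.5.2.1 states: "All the secondary efficacy endpoints will be analyzed in subjects with baseline blood eosinophil counts $\geq 220/\mu\text{L" or more.
- Section 1.2 names a boundary of at least 220/µL "used for the primary and secondary efficacy analyses".

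**The concern.** The 10 mg comparison carries a formal claim of error control, so its population is part of the confirmatory test and has to be fixed before unblinding. The protocol fixes it twice, differently, and the synopsis cites the very section that contradicts it. An analysis plan could adopt one reading, but it would then depart from one of the two protocol statements.

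The populations are not interchangeable. The group with at least 300/µL is smaller, and its true effect may differ, since section 1.2 reports of the earlier study: "The greatest improvements in the annual exacerbation rate were observed in patients with increasing blood eosinophils". The two readings can therefore give different estimates and different decisions for 10 mg. If the choice were still open when the data were unblinded, the 0.05 claim for 10 mg would fail.

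**Working it through.** **Is 300/µL a deliberate exception?** Nothing in the text supports that.

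- No passage gives a reason for a separate 10 mg population.
- Section 8.5.1 specifies: "The model will include covariates of treatment group, eosinophil cohort (220-299" or at least 300/µL). In subjects with at least 300/µL this covariate has a single level.
- The whole group with at least 300/µL is not among the descriptive subgroups in 8.5.1 and 8.5.2.1, which list 300-449/µL and at least 450/µL separately.
- Amendment 3 is consistent with an oversight. It records the move to 220/µL for the 10 mg sentence in the synopsis, but within the testing strategy of section 8.5 only for the 30 mg and 100 mg sentence. The contradiction itself rests on current text alone.

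**Inputs from section 8.2.** Placebo rate 1.0 per 56 weeks, shape k = 0.4, dropout 10%, 30% reduction for 30 mg and 100 mg, 348 per arm for power, 368 per arm recruited at or above 220/µL. I take 10% dropout as 95% mean exposure, so µ0 = 0.95 and µ1 = 0.95 × 0.70 = 0.665.

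**Formula.** Var(log rate ratio) = [(1/µ0 + k) + (1/µ1 + k)]/n = [(1.053 + 0.4) + (1.504 + 0.4)]/n = 3.356/n. Effect: −ln 0.70 = 0.3567.

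**The protocol's own figure.** With n = 348, SE = √(3.356/348) = 0.0982. At two-sided 4% (critical value 2.054), power for one dose is Φ(0.3567/0.0982 − 2.054) = 94.3%. For both doses together, with correlation 0.43 from the shared placebo arm, it is 89.8% (91.1% with full exposure; 90.3% in 2,000 simulated trials). Deducting about 2% for futility gives about 88% to 89%. The stated 90% is reproduced within 2 points.

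**10 mg at two-sided 5%, with 30% assumed for 10 mg and equal in both cohorts.** In at least 220/µL, n = 368 gives SE 0.0955 and power Φ(0.3567/0.0955 − 1.960) = 96.2%. The split at 300/µL is left to the SAP, so the share f of 220-299/µL subjects among the 368 is assumed.

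| f | n per arm, ≥300 | SE | Power, ≥300 | Readings disagree |
|---|---|---|---|---|
| 15% | 313 | 0.1036 | 93% | 4% |
| 25% | 276 | 0.1103 | 90% | 7% |
| 35% | 239 | 0.1185 | 85% | 12% |
| 45% | 202 | 0.1289 | 79% | 18% |

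The last column comes from 2,000,000 draws per row. The two cohort estimates are drawn independently and combined by inverse variance for the at least 220/µL analysis.

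**Unequal effects.** Keep a rate ratio of 0.70 in at least 300/µL, so power there is as in the table. For at least 220/µL, take the inverse-variance weighted mean of the two log rate ratios.

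- Rate ratio 0.85 in 220-299/µL (assumed): power in at least 220/µL is 93/90/86/81%, about the same as in at least 300/µL.
- No effect in 220-299/µL (assumed): 88/78/66/51%. At f = 25%, for example, the weighted effect is 0.2575 with SE 0.0937, and Φ(0.2575/0.0937 − 1.960) = 78%.

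The direction of the power difference thus depends on the unknown effect in 220-299/µL.

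**Type I error if either population could be chosen after unblinding.** Under the null the two statistics have correlation √(1 − f) = 0.922/0.866/0.806/0.741. The chance that at least one is significant at two-sided 5% is 6.8/7.3/7.8/8.1%. The chance of a false benefit is 3.4/3.7/3.9/4.1% instead of 2.5%.

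**The case against.** The best opposing case concerns weight, because the contradiction itself cannot be explained away.

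- The protocol assumes a 30% reduction for 30 mg and 100 mg only. It states no effect or power for 10 mg, and section 1.2 calls doses of 10 mg or less likely suboptimal. This stands: 30% for 10 mg is a borrowed assumption and the power figures are illustrations.
- The cohort split is also assumed, and with a rate ratio of 0.85 in 220-299/µL the two populations have about equal power. This stands: no loss of power is established.
- No passage plans a choice of population after unblinding, and section 8.1 keeps everyone involved in the analysis blinded until database lock. This stands: either population, fixed in advance, keeps 0.05 for the 10 mg tests, and 6.8% to 8.1% is not an error rate of the plan.
- A one-level covariate would simply drop out of the model, and 8.5.1 and 8.5.2.1 name the analysis population rather than the gatekeeping procedure. This is true, but the synopsis names the procedure, the 10 mg dose and at least 220/µL together, and cites section 8.5.
- The protocol openly says that error is not controlled across all three doses and does not power 10 mg. That limits the consequence, but the 0.05 claim for 10 mg on its own remains.

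**Conclusion.** The concern holds. Current text gives one formally error-controlled test two populations, and the apparent intent is at least 220/µL, because the section 8.5 sentence stands alone against the synopsis, 1.2, 8.5.1 and 8.5.2.1. It is wrong as written and should be fixed.

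What is established is the ambiguity. Its practical size depends on the assumed cohort split and the assumed 10 mg effect: the readings disagree on significance in about 4% to 18% of trials when the effect is the same in both cohorts. The sample size, the futility rule and the 30 mg and 100 mg tests are not affected.

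**What to change.** Before unblinding, change the population in the 10 mg sentence of section 8.5 from at least 300/µL to at least 220/µL, so that it agrees with the synopsis, 8.5.1 and 8.5.2.1. The model covariate then fits the tested population and the 0.05 claim refers to one defined test. The cost is a one-line protocol correction, with no additional patients or data.

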8.5.1 Primary analysis method(s)

The primary efficacy variable is the annual COPD exacerbation rate and the primary analysis is to compare the annual COPD exacerbation rate of each benralizumab dose group with placebo in subjects with baseline blood eosinophil counts $\geq 220/\mu\text{L}$.

For each of the three benralizumab dose groups, the null hypothesis is that the exacerbation rate on benralizumab is equal to the exacerbation rate on placebo. The alternative hypothesis is that the exacerbation rate on benralizumab is not equal to the exacerbation rate on placebo, i.e.:

H₀: Rate ratio (benralizumab vs. Placebo) = 1

H_a: Rate ratio (benralizumab vs. Placebo) \neq 1

Exacerbation rate in each of the three benralizumab dose groups will be compared to exacerbation rate in the placebo group using a negative binomial model. The response variable in the model will be the number of COPD exacerbations over the 56-week treatment period. The model will include covariates of treatment group, eosinophil cohort (220-299/ μL or $\geq 300/\mu\text{L}$), country, background therapy (ICS/LABA, LABA/LAMA, or ICS/LABA/LAMA), and the number of exacerbations in the year before the study. The logarithm of the follow-up time will be used as an offset variable in the model.

The estimated treatment effect (i.e., the rate ratio of benralizumab versus placebo), corresponding 95% confidence interval (CI), and two-sided p-value for the rate ratio will be presented. In addition, the exacerbation rate and the corresponding 95% CI within each treatment group will be presented.

In addition, the exacerbation rate will also be summarized in subjects with baseline blood eosinophil counts $< 220/\mu\text{L}$, $< 150/\mu\text{L}$, 150-219/ μL , 220-299/ μL , 300-449/ μL , and $\geq 450/\mu\text{L}$ separately for descriptive purpose only.

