1. INTRODUCTION

1.1 Background and rationale for conducting this study

Chronic obstructive pulmonary disease (COPD) is a significant cause of morbidity and mortality worldwide. In contrast to other chronic diseases, COPD is increasing in prevalence and is projected to be the third-leading cause of death and disability worldwide by 2020 (Global Initiative for Chronic Obstructive Lung Disease (GOLD 2013)).

Acute exacerbations of COPD (AECOPD) are responsible for a large portion of the economic burden of COPD. An AECOPD is defined as a sustained worsening of the patient's condition, from the stable state and beyond normal day-to-day variations, that is acute in onset and necessitates a change in regular medication in a patient with underlying COPD (Rodríguez-Roisin R 2000). In addition to a substantial economic burden, AECOPD is also responsible for much of the morbidity and mortality from COPD. Patients with frequent AECOPD show associated increased inflammation and accelerated decline in lung function as compared to patients with infrequent exacerbations (Donaldson et al 2002).

While airway inflammation in COPD has been traditionally described as being predominately neutrophilic, elevated blood and sputum eosinophils have been reported in a subset of COPD patients (Saha and Brightling 2006; Bafadhel et al 2011). Approximately 30-40% of patients with COPD have elevated levels of eosinophils in the airway as measured by sputum induction or bronchoalveolar lavage (BAL; Brightling et al 2000; Brightling et al 2005; Pizzichini et al 1998; Leigh et al 2006; Saha and Brightling 2006). The prevalence of elevated blood eosinophils in COPD has been less well characterized; however, blood eosinophils have been reported to be an accurate predictor of >3% sputum eosinophils in COPD (Bafadhel et al 2011).

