Subjects should avoid engaging in strenuous exertion for at least 30 minutes prior to spirometry measurements. Subjects should avoid eating a large meal for at least 2 hours prior to spirometry measurements at the centre. Forced expiratory manoeuvres should be performed with the subject seated in an upright position. If this is not comfortable for the subject,

standing is permitted. The same position should be used by the subject for each forced expiratory manoeuvre from enrolment throughout the study. The head must not be tilted during manoeuvres and the thorax should be able to move freely; hence tight clothing should be loosened. A nose-clip should be used for the manoeuvre. The subject from enrolment throughout the study should use mouthpieces of the same dimension and shape.

The forced expiratory manoeuvre (FEV₁ and FVC) should start with a maximal inspiration and then followed by a fast and forceful expiration that should last for at least 6 seconds. It is important to encourage the subject to continue the expiration to be fast and forceful throughout the manoeuvre. Ensure that none of the following has occurred: coughing during the first second, glottis closure, leak or obstruction of the mouthpiece (by the tongue).

Multiple forced expiratory efforts (at least 3 but no more than 8) will be performed for each centre spirometry session and the 2 best efforts that meet the ATS/ERS acceptability and reproducibility criteria will be recorded. The best efforts will be based on the highest FEV₁. The absolute measurement (for FEV₁ and FVC), and the percentage of predicted normal value (Quanjer et al 2012) will be recorded. The highest FVC will also be reported regardless of the effort in which it occurred (even if the effort did not result in the highest FEV₁).

Post-bronchodilator spirometry

Post-BD spirometry will be performed at V2 for all subjects (to evaluate inclusion criterion 3, see section 3.1).

Maximal bronchodilation will be induced using 4 inhalations of albuterol (90 µg metered dose) or salbutamol (100 µg metered dose) with or without a spacer device within 30 minutes ± 15 minutes of the final pre-BD spirometry measurement. Post-BD spirometry will be performed 20-30 minutes later. If a subject cannot tolerate 4 puffs of beta agonist, a lower number of inhalations may be considered at the investigator's clinical judgment.

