8.2 Sample size estimate

The study will recruit subjects with blood eosinophil counts $<220/\mu\text{L}$, $220\text{-}299/\mu\text{L}$, and $\geq 300/\mu\text{L}$. The approximately 2:1 ratio between $\geq 220/\mu\text{L}$ and $<220/\mu\text{L}$ allows analysis of the primary population for subjects most likely to respond to benralizumab (i.e. $\geq 220/\mu\text{L}$), while still including subjects below this threshold in order to help understand efficacy and safety in this group. The study is powered for the exacerbation rate comparisons of the subjects with blood eosinophils $\geq 220/\mu\text{L}$ (primary efficacy analysis).

For the primary endpoint annual COPD exacerbation rate, 348 subjects with baseline blood eosinophil counts $\geq 220/\mu\text{L}$ per treatment arm (1392 total) will need to be randomised to achieve 90% power of detecting a 30% reduction in both the 30mg and 100mg benralizumab dose groups versus placebo based on a Hochberg Procedure (Hochberg 1988). This calculation has assumed two-sided 4% alpha level tests, an annual placebo rate of 0.93 events/subject (1.0 events/subject/56 weeks), a negative binomial shape parameter of 0.4, and a dropout rate of 10%. The sample size calculation is based on simulations and has accounted for the power loss from a proposed futility analysis (Section 8.5.6).

As stated previously an approximately 2:1 ratio will be used for subjects with blood eosinophil counts $\geq 220/\mu\text{L}$ and $<220/\mu\text{L}$. Therefore this study will randomise 174 subjects/arm (696 total) with baseline blood eosinophil counts $<220/\mu\text{L}$. An additional 20 subjects/arm will also be recruited to the 220-299/ μL cohort to better characterize patients within this cohort. This addition results in 368 subjects/arm in the $\geq 220/\mu\text{L}$ cohort (1472 total). A total of 2168 subjects are expected to be randomised in this study. Details of the estimated numbers of recruited subjects/arm in each cohort ($<220/\mu\text{L}$, $220\text{-}299/\mu\text{L}$, $\geq 300/\mu\text{L}$) are described in the SAP.

The sample size necessary to achieve a stated power (90% in our case) in this study is calculated based on the estimate of overall exacerbation rate and shape parameter from the negative binomial model (Section 8.5.1). In order to better estimate the overall exacerbation

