8.5 Methods for statistical analyses

The primary analysis of the primary and key secondary endpoints will include all data captured during the 56-week treatment period, regardless of whether study treatment was prematurely discontinued, or delayed, and/or irrespective of protocol adherence.

Demography and baseline characteristics will be summarized by treatment group for the full analysis set. In the event that there are major differences between the full analysis set and safety analysis set, these summaries will also be repeated for the safety analysis set.

Testing strategy to account for multiplicity considerations

To account for multiplicity to test the primary (exacerbation) and two key secondary endpoints (FEV₁ and SGRQ) for each of the 30mg and 100mg dose groups (for subjects with baseline blood eosinophils $\geq 220/\mu\text{L}$) a testing strategy will be followed to control the overall type I error rate at level 0.05. The testing strategy will be according to the following gate keeping procedure:

Step 1: Perform the two tests of annual COPD exacerbation rate (one test for each dose vs. placebo) at the family wise error rate (FWER) of 0.04 using a Hochberg Procedure ([Hochberg](#))

[figure not shown]
1988). If both p-values are less than 0.04, then proceed to Step 2; else if the smaller p-value is less than 0.02 then proceed to Step 2a; otherwise no null hypothesis is rejected

Step 2: Test the two key secondary endpoints for both doses as one family at the FWER of 0.05 using a Holm Procedure (Holm 1979).

Step 2a: Test the two secondary endpoints for the smaller-p-value dose at the FWER of 0.01 using a Holm Procedure.

The gatekeeping procedure is also shown in the diagram below:

Figure 4 Gatekeeping Procedure

Since the correlation of the two test statistics for COPD exacerbation rate in the Step 1 is positive, the FWER of the Hochberg Procedure is strongly controlled at 0.04. The overall FWER of the gatekeeping procedure is strongly controlled at 0.05.

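### The primary exacerbation model has no lung-function term, although Visit 2 FEV1 is collected for eligibility; adding it is an optional refinement worth at most about 4% of variance

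*Protocol*

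**What the plan says.** Section 8.5.1 specifies the covariates: "The model will include covariates of treatment group, eosinophil cohort" (220-299/µL or ≥300/µL), country, background therapy (three classes) and the prior-year exacerbation count. No FEV1 term appears.

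Section 8.5.2.1 uses the same covariates in the logistic model for at least one exacerbation and in the Cox model for time to first exacerbation. It refers back to 8.5.1 for the rate of exacerbations with an emergency room visit or hospitalisation and for the healthcare-encounter rates. Baseline FEV1 is a covariate only in the model for change in FEV1.

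On spirometry, section 5.1.2 states: "Post-BD spirometry will be performed at V2 for all subjects". The value decides inclusion criterion 3 (section 3.1), which admits patients above 20% and up to 65% of predicted. Section 4.1.1 describes severity as resting on background medication, spirometry and exacerbation history. Section 3.3 stratifies randomisation by country and by eosinophil count at 300/µL, not by lung function.

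**The concern.** Of the three severity markers named in section 4.1.1, the primary model uses two (background therapy and exacerbation history) and leaves out the third. Section 1.2 also defines the moderate to very severe population by post-bronchodilator FEV1, so FEV1 is the protocol's own severity scale. Entry criterion 4 narrows the exacerbation history at its lower end (at least two moderate or one severe event), while FEV1 may span 45 points.

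If FEV1 predicts exacerbation rate beyond the covariates already present, that variation stays in the negative binomial dispersion and slightly widens the intervals of the primary rate ratios. A chance difference between arms in FEV1 would also go uncorrected.

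**Working it through.** **Inputs from the protocol (sections 8.2, 8.5 and 8.5.6)**
- 348 patients per arm with eosinophils ≥220/µL, "to achieve 90% power of detecting a 30% reduction in both the 30mg and 100mg benralizumab dose groups versus placebo".
- Placebo rate 0.93 per year, or 1.0 per 56 weeks; rate ratio 0.70, so the active mean is 0.70.
- "a negative binomial shape parameter of 0.4", read as dispersion k with variance = μ + kμ².
- "This calculation has assumed two-sided 4% alpha level tests", with the Hochberg rule: "If both p-values are less than 0.04, then proceed to Step 2; else if the smaller p-value is less than 0.02" decides the alternative branch.
- Dropout 10%. With uniform dropout times (an assumption), mean exposure is 0.95 of 56 weeks.

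**Reproducing the plan's figure without FEV1**

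Var(log RR) = [(1/μ0 + k) + (1/μ1 + k)]/n. At exposure 0.95, μ0 = 0.95 and μ1 = 0.665, so

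(1/0.95 + 0.4) + (1/0.665 + 0.4) = 1.453 + 1.904 = 3.356, and SE = √(3.356/348) = 0.0982.

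Per comparison, ln(0.70)/SE gives 3.632. Subtracting the critical value 2.054 leaves 1.578, a power of 0.943. The two comparisons share the placebo arm, with correlation 1.453/3.356 = 0.433. The bivariate normal probability that both are significant at 0.04 is 0.898.

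A simulation of gamma-Poisson counts with the Hochberg rule and the futility look gave 0.898 (0.902 without the look). Futility stops were 1.8% under the alternative and 54.9% under the null, against the stated ~2% and ~55%. It assumed that the companion study contributes equally to the look. Reading the shape as 1/k (k = 2.5) gives power of about 0.48, so the dispersion reading is the right one.

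**Adding FEV1**

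The link between FEV1 and exacerbation rate is not in the documents. Assumed: a rate ratio of 1.00 to 1.20 per 10 points lower FEV1 % predicted, and an SD of 11 to 12 points. A flat spread over 20-65 would have SD 45/√12 = 13.0, so 11-12 is plausible.

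The log-rate SD due to FEV1 is s = ln(rate ratio) × SD/10. The second moment of the patient-level rate multiplier is 1 + k = 1.4 = exp(s²)(1 + k_res), hence k_res = 1.4/exp(s²) − 1.

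| Rate ratio per 10 points | SD | s² | k_res | Variance change | Both-dose power |
|---|---|---|---|---|---|
| 1.00 | any | 0 | 0.400 | 0 | 0.898 |
| 1.10 | 11 | 0.0110 | 0.385 | −0.9% | 0.901 |
| 1.15 | 11 | 0.0236 | 0.367 | −2.0% | 0.905 |
| 1.20 | 11 | 0.0402 | 0.345 | −3.3% | 0.909 |
| 1.20 | 12 | 0.0479 | 0.335 | −3.9% | 0.911 |

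The last row in full: 1/0.95 + 1/0.665 + 2 × 0.335 = 3.226, and 3.226/3.356 = 0.961. This equals 348/0.961 − 348 ≈ 14 patients per arm. These are upper bounds for each slope, because the formula treats the whole FEV1 signal as independent of the existing covariates. Beyond the assumed range, a rate ratio of 1.30 with SD 13 would give −9% and a power of 0.928.

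**Chance imbalance**

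At SD 12, the SE of the between-arm difference in mean FEV1 is 12 × √(2/348) = 0.91 points. At a rate ratio of 1.20 the slope is ln(1.20)/10 = 0.0182 per point, so a two-SE imbalance shifts the log rate ratio by 0.033, about a third of its SE (0.033/0.098 = 0.34). At 1.10 the shift is 0.017, and at 1.00 it is zero. This is largely the same gain seen in a single trial, so it should not be added to the variance reduction.

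**The case against.** The strongest case against is that nothing here is wrong. The model already carries the endpoint's own history, the treatment tier, country and eosinophil cohort, which is a standard and defensible set. Leaving out a prognostic covariate in a randomised comparison neither biases the test nor inflates type I error. Stated power is met without FEV1. The planned 368 per arm gives 0.916 unadjusted, more than adjustment yields at 348 per arm anywhere in the assumed range. Section 8.2 also provides a blinded re-estimation of the shape parameter. The same argument could be made for other baseline variables. All of this stands and limits the point to an optional improvement.

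Three stronger readings are tempting, and the documents do not support them:
- A reader might infer that the model ignores disease severity. It does not: background therapy and prior exacerbations are two of the protocol's own three markers. Only lung function is absent.
- A reader might take section 1.1 as evidence that baseline FEV1 predicts exacerbations. It says: "Patients with frequent AECOPD show associated increased inflammation and accelerated decline in lung function as compared to patients with infrequent exacerbations". That concerns later decline in relation to exacerbation frequency, not baseline level as a predictor of rate. A wide entry range is not evidence of prognostic value either.
- A reader might infer that power is lost against the stated target. The sizing mentions no covariate adjustment, and its 90% is reproduced with k = 0.4 and no covariates.

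What remains is that FEV1 differs from an arbitrary extra variable: the protocol itself names it as a severity marker, uses it to define the population and obtains it for eligibility.

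**Conclusion.** The point holds as a minor, optional refinement. The primary model and the exacerbation models that reuse its covariates omit a severity marker the protocol names and already collects. The expected benefit is a 0 to 4% lower variance of the log rate ratio, or 0 to about 1 point of both-dose power (0.898 to between 0.909 and 0.911 at the top of the range), plus removal of any chance imbalance in FEV1. This rests on an assumed rate ratio of 1.00 to 1.20 per 10 points and an SD of 11 to 12, neither of which the documents give. The honest range includes no gain at all, and overlap with prior exacerbations and background therapy would shrink any gain. The validity of the primary test and the adequacy of the sample size are not in question.

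**What to change.** Add continuous Visit 2 post-bronchodilator FEV1 % predicted to the covariates in section 8.5.1 and in the exacerbation models of section 8.5.2.1 built on it, and fix this in the protocol or SAP before unblinding. Name the measurement explicitly, because section 8.4.1.4 defines baseline FEV1 differently, as the pre-bronchodilator value at Visit 4.

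The cost is one degree of freedom per model and a text change. No new data are needed and the sample size need not change. In the logistic and Cox models an added prognostic covariate also changes the quantity estimated, since odds and hazard ratios are conditional on the covariates, so the variance figures above apply to the rate models only.
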